The disease begins with a malignant change to the B-cell during its maturation so that it continues to reproduce more malignant B-cells, resulting in an overproduction of monoclonal IgM antibody. Clinical manifestations of WM include cytopenias resulting from bone marrow infiltration by lymphoplasmacytic cells and IgM paraprotein related symptoms such as cryoglobulinemia, the cold agglutinin syndrome, demyelinating neuropathy, and symptomatic hyperviscosity.

Waldenström's macroglobulinemia, which constitutes 1–2% of hematologic malignancies, is an orphan indication; the overall incidence of WM is 3 per million persons per year with approximately 1500 new cases diagnosed in the US each year. The most recognized risk factor for developing WM is IgM Monoclonal Gammopathy of Undermined Significance (MGUS), which confers a 46-fold higher relative risk compared to the general population. Recently, a somatic mutation of the MYD88 gene (L265P) has been identified that appears to drive WM growth and proliferation.

WM remains an incurable disease with variability in outcome. Approximately 75% of patients are symptomatic and therefore require treatment to control symptoms related to tumor burden. The symptoms and signs of WM may vary but are usually related to signs of bone marrow infiltration such as anemia or cytopenias, or symptoms and signs due to hyperviscosity resulting from elevated IgM levels in the serum. Asymptomatic patients should be observed and serum IgM levels alone are not a basis for treatment.

Anemia is the most frequent cytopenia requiring medical management, and with progression of their illness, WM patients become dependent on repeated blood transfusions for refractory anemia. These supportive measures do not treat the underlying biology of the disease and are often associated with iron overload.

Factors associated with a poor prognosis include advanced age, high beta 2-microglobulin (β_2M), low albumin, cytopenias, serum IgM monoclonal protein, and organomegaly. An international prognostic scoring system for newly diagnosed WM patients was recently developed

(Morel 2009) based on 5 factors: Age (>65 years) β_2 M (>3mg/L), anemia (Hb \leq 11.5 g/dL), thrombocytopenia (\leq 100 x 10⁹/L), IgM monoclonal gammopathy (>7.0 g/dL) with 5-year survival ranging from 36% to 87% in high and low-risk patients, respectively (Table 1).

Table 1: WM International Prognostic Scoring System (IPSS)¹

	Low-risk	Intermediate-risk	High-risk

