10.6.2.3. Time to Next Treatment

Time-to-next treatment (TTnT) is measured from the date of randomization to the start date of any subsequent WM treatment. Subjects without subsequent treatment will be censored at the date of the last study visit. Detailed censoring rules will be included in the SAP. The analysis of TTnT will be analyzed using stratified or unstratified log-rank test as appropriate.

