10.6.2.4. Overall Survival (OS)

Overall survival (OS) is measured from the date of randomization to the date of the subject's death from any cause. Overall survival will be analyzed using the stratified log-rank test for treatment comparison. If the subject is alive or the vital status is unknown, the subject will be censored at the date the subject was last known to be alive. The overall survival distribution and median overall survival with its 95% CI will be estimated using the Kaplan-Meier product-limit method. The same subgroup analysis of PFS may be performed for overall survival if the number of events within each subgroup is sufficient. The exploratory analysis on the effect of cross-over on overall survival may be described in the SAP (eg, detailed censoring rules) and performed as appropriate.

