1.6. Testing Procedure and Level of Significance

Interim Analysis

In order to preserve the study wise 2-sided type I error rate of 0.05, the 2-sided significance level for PFS will be 0.015 at 50 PFS events for the interim analysis, based on O'Brien Fleming boundary. However, the alpha spending for PFS will be determined based on the actual information fraction using O'Brien-Fleming boundary at the time of the interim analysis.

If the primary endpoint achieves statistical significance, tests of secondary endpoints will be performed at the 2-sided significance level of 0.05 in a sequential hierarchical manner based on a closed testing procedure. The secondary endpoints will be ranked in sequence according to the hierarchical order specified below. OS will not be tested at interim analysis and will be tested at study closure.

- 1.) ORR
- 2.) TTnT
- 3.) Rate of sustained hemoglobin improvement
- 4.) Proportion of subjects with \geq 3 points increase from baseline by Week 25 in fatigue experience score
- 5.) OS

Final Analysis

The 2-sided significance level for the final analysis of primary endpoint (PFS) will be adjusted to account for interim alpha spending so the overall 2-sided significance level for the study will be preserved at 0.05. Tests of secondary endpoints will be performed using the same approach for the interim analysis.

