4. EFFICACY AND SAFETY ANALYSES

4.1. Efficacy Analyses

Treatment Arms A and B

Efficacy endpoints and analysis methods for the randomized treatment arms (Arms A and B) are summarized in Table 2.

The following two randomization stratification factors will be used for the stratified analysis/test: WM IPSS assessed at screening (low, intermediate, high) and number of prior systemic treatment regimens $(0, \ge 1)$. Due to limited number of subjects with ≥ 3 prior systemic treatment regimens, subjects with 1-2 or ≥ 3 prior systemic treatment regimens will be categorized into one subgroup (i.e. ≥ 1). All the stratified tests will be based on the randomization stratification factors as recorded in IWRS.

Open-Label Substudy Treatment Arm C

For the open-label Arm C, the efficacy outcome will be analyzed separately from the randomized treatment arms. Time to event variables (e.g. PFS, TTnT, OS, DOR) will be analyzed using Kaplan-Meier estimate. For categorical variables (e.g. ORR, rate of sustained hemoglobin improvement, CRR), 95% confidence intervals (CIs) will be calculated based on the exact binomial distribution. For continuous variables (e.g. IgM, lymph node and spleen measures, tumor involvement of bone marrow), descriptive statistics will be calculated. No comparator analysis will be done with Arms A or B.

Note that date of randomization is not applicable for Arm C subjects, therefore date of the first dose of ibrutinib will be used in calculating efficacy variables.

Table 2: Summary of Efficacy Analyses to be Performed for Arms A and B

Endpoint	Definition	Analysis Methods			
Primary Endpoint					

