PFS assessed by IRC	Time from the date of randomization to the date of first IRC-confirmed disease progression (PD) or date of death due to any cause, whichever occurs first, regardless of the use of subsequent antineoplastic therapy prior to documented PD or death. For subjects who do not have IRC-confirmed PD and not known death as of clinical data cutoff, PFS is censored at the date of the last evidence of no progression by IRC.	 The treatment effect of ibrutinib + rituximab (Arm A) compared to placebo + rituximab (Arm B) will be tested with a stratified log rank test adjusted for 2 randomization stratification factors. The hazard ratio and its 95% confidence interval (CI) based on a Cox regression model stratified by the 2 randomization stratification factors will be calculated. Kaplan-Meier analysis for PFS distribution; median PFS estimated with 2-sided 95% CI. Sensitivity Analyses: Subjects who received subsequent antineoplastic therapy are censored at the last disease assessment showing no evidence of PD before the use of subsequent therapy: same analyses as above. Subjects who missed ≥2 consecutively planned disease assessments immediately before IRC-confirmed PD or death are censored at the last disease assessment prior to documented PD or death: same analyses as above. Investigator assessed PFS: same analyses as above. IRC-assessed PFS by unstratified log-rank test and unstratified Cox regression model. 			
Secondary Endpoints					
ORR assessed by IRC	Proportion of subjects achieving a best overall response of confirmed complete response (CR), very good partial response (VGPR), or PR per the IRC assessment at or prior to initiation of subsequent antineoplastic therapy.	ORR will be compared between the two randomized treatment arms (ibrutinib + rituximab vs. placebo + rituximab) using Cochran-Mantel-Haenszel (CMH) chi- square test, adjusted for the 2 randomization stratification factors. 95% CI for the rate ratio will be calculated. Sensitivity Analyses: Investigator assessed ORR: same analyses as above. Subgroup Analyses: Rate ratio and its 95% CI for each subgroup of selected variables (e.g. prior treatment history, MYD88 L265P mutational status).			
Time to next treatment	Time from the date of randomization to the start date of any subsequent WM treatment.	Same as PFS: stratified log-rank test, stratified Cox regression model, and Kaplan-Meier analysis.			

PCYC-1127-CA Statistical Analysis Plan

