Endpoint	Definition	Analysis Methods	
(TTnT)	Subjects without subsequent treatment are censored at the date of the last study visit.		
Rate of sustained hemoglobin improvement	Proportion of subjects achieving a sustained improvement in hemoglobin (Hgb) at or prior to initiation of subsequent antineoplastic therapy. Hgb improvement is defined as an increase of ≥ 2 g/dL over baseline regardless of baseline value, or an increase to >11 g/dL with a ≥ 0.5 g/dL improvement if baseline is ≤ 11 g/dL. Sustained Hgb improvement is defined as improvement that is sustained continuously for ≥ 56 days (8 weeks) without blood transfusion or growth factors.	The two randomized treatment arms will be compared (ibrutinib + rituximab vs. placebo + rituximab) using chi- square test. 95% CI for the rate ratio will be calculated. Subgroup Analysis: Chi-square test for subjects with Hgb ≤ 11 g/dL at baseline.	
Proportion of subjects with ≥ 3 points increase from baseline by Week 25 in fatigue experience score	Proportion of subjects with $a \ge 3$ points increase from baseline in fatigue experience score at any time point at or prior to initiation of subsequent antineoplastic therapy by Week 25. Fatigue experience score is calculated from the FACT-An 5 items (HI7, HI12, An1, An2, An5) assessing fatigue symptoms.	The two randomized treatment arms will be compared (ibrutinib + rituximab vs. placebo + rituximab) using chi- square test. 95% CI for the rate ratio will be calculated.	
Overall survival (OS)	Time from the date of randomization to the date of death from any cause. For subjects who were not known to have died at or prior to the clinical cutoff date, OS is censored on the date last known alive.	Unstratified log-rank test, unstratified Cox regression model, and Kaplan-Meier analysis. Exploratory analysis adjusting the crossover effect may be performed, if needed.	
Exploratory E	ndpoints		
Time to sustained hemoglobin improvement	Time from the date of randomization to the initial date of sustained hemoglobin improvement.	Descriptive summary statistics for subjects who achieved sustained hemoglobin improvement.	
DOR by IRC, DOR by investigator	Time from the date of initial documentation of a response (PR or better) to the date of first documented evidence of PD or death for responders (PR or better). The same censoring rules for PFS are used for DOR.	Kaplan-Meier analysis	

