5. MODIFICATION OF ANALYSIS TO THE PROTOCOL

Below is the major change made to the analyses in the protocol:

• Proportion of subjects with ≥ 3 points increase from baseline by Week 25 in fatigue experience score is added as one of the secondary endpoints to evaluate the treatment effect on fatigue symptoms.

In addition, Hgb, lymph nodes and spleen measures, and tumor involvement of bone marrow are included for exploratory analyses. For the exploratory endpoint time to sustained hemoglobin improvement, descriptive statistics will be calculated for subjects who achieved sustained hemoglobin improvement. Kaplan-Meier analysis and log-rank test will not be performed. For PRO data, exploratory analyses will be conducted for rate of clinically meaningful improvement and time to improvement.

6. REFERENCES

FACT-An Scoring Guidelines (Version 4). www.facit.org

FACIT-Fatigue Subscale Scoring Guidelines (Version 4). www.facit.org

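### The SAP tests overall survival without stratification, although the protocol fixes a stratified log-rank test; no reason is given and the change is not recorded

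*SAP*

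**What the plan says.** **Protocol.** Section 10.6.2.4: "Overall survival will be analyzed using the stratified log-rank test for treatment comparison". Where the protocol meant to leave the choice open it said so. For time to next treatment (Section 10.6.2.3): "The analysis of TTnT will be analyzed using stratified or unstratified log-rank test as appropriate". Section 10.6.2.2 gives the same latitude for time to hemoglobin improvement. For PFS, Section 10.6.1 names a log-rank test without mentioning strata.

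**SAP, 13 October 2017.** Section 4.1 introduces the strata with "The following two randomization stratification factors will be used for the stratified analysis/test": IPSS in three levels, and prior regimens as 0 or at least 1. In Table 2, PFS has a stratified log-rank test and stratified Cox model, with the unstratified versions as sensitivity only: "IRC-assessed PFS by unstratified log-rank test and unstratified Cox regression model". TTnT follows PFS, and ORR uses a CMH test on the same two factors. For OS the entry is "Unstratified log-rank test, unstratified Cox regression model, and Kaplan-Meier analysis". No stratified OS analysis appears, even as sensitivity.

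Section 1.6 places OS fifth and last in the tested hierarchy and adds: "OS will not be tested at interim analysis and will be tested at study closure". Section 5 opens with "Below is the major change made to the analyses in the protocol", names the added fatigue endpoint, then lists exploratory additions and a dropped log-rank test for time to hemoglobin improvement. OS is not mentioned. The later SAP for the Final CSR refers back to the 2017 SAP for analyses already done and does not revisit the randomized OS comparison.

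**The concern.** The two governing documents name different tests for an endpoint inside the type I error-controlled hierarchy. The OS p-value and hazard ratio at study closure therefore depend on which document is followed. OS is the one endpoint for which the protocol fixed stratification outright, and the only formally tested time-to-event endpoint for which the SAP removes it.

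IPSS is both a randomization factor and a survival score. Protocol Section 1.1 reports "5-year survival ranging from 36% to 87% in high and low-risk patients, respectively". When randomization is balanced on a strongly prognostic factor, a test that ignores the factor uses a variance that is too large: it becomes conservative, loses power, and its hazard ratio moves toward 1. An undocumented choice of test for a survival endpoint also invites questions at readout that a line of SAP text would prevent.

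**Working it through.** **1. The texts side by side**

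| Endpoint | Protocol | SAP Table 2 |
|---|---|---|
| PFS | log-rank, strata not mentioned | stratified; unstratified as sensitivity |
| TTnT | either form allowed | stratified |
| OS | stratified, no option | unstratified only |

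The only reasoning about strata in SAP Section 4.1 concerns merging 1–2 with ≥3 prior regimens. It does not bear on dropping strata for OS.

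**2. The plan's own figure.** The plan states an event target only for PFS. Freedman's formula at HR 0.5, two-sided 0.05 and 80% power gives (1.960 + 0.842)² × (1.5/0.5)² = 7.85 × 9 = 70.6, so 71 events, as stated. No deaths, effect or power are stated for OS, so what follows is an illustration on assumed inputs.

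**3. Inputs**
- From the documents: 150 subjects, 1:1; 12 per month, so 150/12 = 12.5 months of accrual; study end about 3 years after the last randomization; IPSS mix 27/38/35% and 5-year survival 87/68/36% (Protocol Table 1); control median PFS 15 months; two-sided 0.05.
- Assumed: the OS hazard ratio; half of subjects previously treated; the share of Arm B crossing over; exponential survival; no dropout; permuted blocks of 4 within six strata (IPSS × prior regimens 0 or ≥1).
- Control hazards, −ln(S₅)/5 per year: 0.0279, 0.0771 and 0.2043 for low, intermediate and high IPSS. The high-to-low ratio is about 7.3.

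**4. Expected deaths at HR 0.5.** Mean follow-up is 36 + 12.5/2 = 42.25 months = 3.52 years. Averaging the two arms' probabilities of death:
- Low: 40.5 × (0.0934 + 0.0479)/2 = 2.9
- Intermediate: 57 × (0.2378 + 0.1270)/2 = 10.4
- High: 52.5 × (0.5130 + 0.3021)/2 = 21.4

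The total is about 34.7. Schoenfeld power at that count is Φ(√(34.7/4) × ln 2 − 1.96) = Φ(0.08) = 53%, close to the simulated stratified value below.

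**5. Simulation.** Each test is Z = ΣU/√ΣV, where U sums (arm − p) and V sums p(1 − p) over deaths, with p the Arm A share of those at risk. The stratified form computes these within the six strata and adds them. There were 20,000 trials per scenario; the Monte Carlo standard error of each difference is at most 0.2 points.

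| Scenario | Unstratified | Stratified | Difference (points) |
|---|---|---|---|
| Table 1 rates, HR 0.5 | 46.1% | 51.0% | +4.9 |
| Table 1 rates, HR 0.7 | 16.3% | 19.6% | +3.3 |
| Table 1 rates, HR 0.8 | 8.4% | 10.9% | +2.5 |
| HR 0.5, prior therapy also prognostic (hazard ×1.5) | 46.5% | 51.9% | +5.4 |
| HR 0.5, half the hazard (about 19 deaths) | 29.3% | 31.3% | +2.0 |
| HR 0.5, 50% of Arm B crosses over at progression | 28.2% | 32.0% | +3.8 |
| HR 0.5, 100% crosses over | 14.0% | 16.8% | +2.8 |
| HR 0.5, 5-year survival 75/65/50% | 47.5% | 47.9% | +0.4 |
| HR 0.5, no gradient (62% in all strata) | 49.3% | 48.9% | −0.4 |
| Size: Table 1 rates, HR 1.0 | 3.4% | 5.0% | – |

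In the crossover rows, crossed-over subjects take the Arm A hazard. At HR 0.5 under Table 1 rates the median estimated hazard ratio is 0.52 unstratified and 0.50 stratified.

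**6. Agreement.** A separate simulation (5,000 trials per hazard ratio, same mix and rates) gave 46.7% against 51.1% at HR 0.5, 17.2% against 21.0% at HR 0.7, and 3.1% against 4.9% at HR 1.0. The two tests reached different significance verdicts in 2.1% of trials at HR 1.0 and 6.4% at HR 0.5.

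**The case against.** - **The SAP is the more specific document.** Protocol Section 10 calls itself a general description and leaves details to the SAP, and the SAP names one OS test without ambiguity. An analyst following the SAP has no choice to make. That is fair, but stratification of OS was not among the details left open, so this remains an unexplained departure.
- **OS is not alone.** The hemoglobin and fatigue proportions are also unstratified in the SAP, and Section 5 also omits the change of the ORR test from chi-square to stratified CMH. Section 5 is therefore not a complete log, and the missing OS entry is weaker evidence of a specific lapse. But the protocol fixed stratification only for OS, and Section 5 does record a dropped log-rank test for a merely exploratory endpoint.
- **The IPSS figures may not carry over.** The protocol says the score was developed in newly diagnosed patients, while this trial also enrols previously treated ones. This stands. With a gentler gradient the difference almost vanishes.
- **Sparse strata could justify the SAP's choice.** About 3 of some 35 deaths would fall in the low-IPSS strata. The reason is plausible, but the SAP does not give it. With about 19 deaths the six-stratum test still did slightly better under Table 1 rates.
- **Changing the test late has its own risk.** The Final CSR SAP shows that the primary analyses had already been run. This bears on how the correction is documented. The stratified test is, however, the one the protocol already specifies.

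**Conclusion.** The concern holds. The protocol requires a stratified log-rank test for OS, the SAP specifies only an unstratified one, and the documents contain no reason and no record of the change.

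The consequence is modest. Type I error is not inflated; under Table 1 rates the unstratified test is conservative (3.4% against a nominal 5%). Stratifying gains about 2 to 5 power points if IPSS is as prognostic as Protocol Table 1 shows, and essentially nothing if the gradient is weak or absent. These figures rest on assumed OS effects, an assumed half previously treated, assumed crossover shares, and survival rates from newly diagnosed patients. OS is last in the hierarchy, so no later test depends on it. The inconsistency should be corrected, mainly so that the OS result at study closure comes from one agreed and documented test.

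**What to change.** Replace the analysis-method entry for OS in SAP Table 2 with:

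> Same as PFS: stratified log-rank test and stratified Cox regression model, using the 2 randomization stratification factors as recorded in IWRS (IPSS; prior regimens 0 vs ≥1), and Kaplan-Meier analysis. Sensitivity: unstratified log-rank test and unstratified Cox regression model.

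If the sponsor prefers to keep the unstratified test as the tested analysis, list the departure from Protocol Section 10.6.2.4 and its reason in SAP Section 5 before the study-closure OS test, and add the stratified analysis as sensitivity. In either case, date the change and state whether OS results by arm had been seen when it was made.

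The cost is SAP wording. The factors and code already exist for PFS and TTnT. If neither factor is prognostic, the six-stratum test gives up about 0.4 power points.

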Clinical laboratory tests	Worst post-baseline toxicity grade, creatinine clearance, abnormal uric acid, liver function abnormalities	Descriptive summary statistics and/or listings; shift from baseline in creatinine clearance, shifts from baseline in aspartate aminotransferase (AST), alanine aminotransferase (ALT) and bilirubin toxicity grade
Vital signs, eye-related symptoms	Blood pressure, heart rate, temperature, respiratory rate, weight, proportion of subjects with new or worsening eye-related symptoms	Descriptive summary statistics by treatment arm and visit. A data listing will be provided for abnormal ophthalmologic exam findings.

Table 3: Summary of Safety Analyses to be Performed for all Treatment Arms

5. MODIFICATION OF ANALYSIS TO THE PROTOCOL

Below is the major change made to the analyses in the protocol:

• Proportion of subjects with ≥ 3 points increase from baseline by Week 25 in fatigue experience score is added as one of the secondary endpoints to evaluate the treatment effect on fatigue symptoms.

In addition, Hgb, lymph nodes and spleen measures, and tumor involvement of bone marrow are included for exploratory analyses. For the exploratory endpoint time to sustained hemoglobin improvement, descriptive statistics will be calculated for subjects who achieved sustained hemoglobin improvement. Kaplan-Meier analysis and log-rank test will not be performed. For PRO data, exploratory analyses will be conducted for rate of clinically meaningful improvement and time to improvement.

6. REFERENCES

FACT-An Scoring Guidelines (Version 4). www.facit.org

FACIT-Fatigue Subscale Scoring Guidelines (Version 4). www.facit.org
